11.3. Protocol Deviations

Protocol deviations are considered any deviation from the CSP relating to a subject, and include the following:

- Inclusion/exclusion criteria deviations
- Dosing deviations (eg, incorrect treatment received, subject was not fasted as per the protocol requirements prior to and after dosing)
- Time window deviations for safety and/or PK assessments
- Subjects receiving prohibited concomitant medications
- Other procedural and study conduct deviations recorded by the Clinical Unit on a protocol deviation log

The criteria for the assessment and reporting of protocol deviations will be stipulated in a separate study specific protocol deviation specification document. This will include a WAD which stipulates tolerance windows for safety and PK assessments. Measurements performed within these tolerance windows will not be considered as protocol deviations and will not be reported.

All protocol deviations will be discussed at the data review meeting prior to database hard lock in order to define the analysis sets for the study.

Important protocol deviations will be listed by subject.

Protocol deviations (missing assessments/visits) related to COVID-19 will be listed separately.

Protocol deviations will be handled in accordance with Parexel SOPs.

For handling of protocol amendments, see Section 8.6.

11.4. Determination of Sample Size

The sample size was chosen to obtain reasonable assessment of relative bioavailability between different formulations of verinurad and/or allopurinol without exposing undue numbers of subjects to the compound at this phase of clinical development. It is estimated that 20 subjects randomised to 5 sequences in a reduced Latin square will provide a 90% CI within 0.7 and 1.43, with a probability of >90% if the estimated treatment ratio is 1 for C_{max}. This is based on an intra-subject variability of 24% for C_{max} of verinurad in Study D5495C00001. Similarly, it is estimated that 20 subjects will provide a 90% CI within 0.8 and 1.25, with a probability of >95% if the estimated treatment ratio is 1 for AUC. This is based on an intra-subject variability of 14.7% for AUC of verinurad in Study D5495C00001.

Twenty-five subjects will be equally randomised to 5 treatment sequences: 12345, 23451, 34512, 45123, and 51234 in order to ensure at least 20 evaluable subjects at the end of the last treatment period.

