3. STUDY DESIGN

3.1. Overall Study Design and Flow Chart

This study will be a single-centre, randomised, open-label, single-dose, 5-period, 5-treatment, crossover study in healthy male and female subjects.

The study will comprise:

- A Screening Period of maximum 28 days.
- Five treatment periods during which subjects will be resident from the morning of Day -2 until at least 72 hours after dosing in Treatment Period 5; discharged on the morning of Day 4 of Treatment Period 5.
- A Follow-up Visit 7 to 14 days after the last dosing.

There will be a minimum washout period of 5 days between each dose administration.

A total of 25 healthy male and female subjects will be randomised into one of 5 treatment sequences to ensure at least 20 evaluable subjects at the end of the last treatment period. Each subject will receive 5 single-dose treatments of verinurad and allopurinol or verinurad alone:

- Treatment 1: verinurad prolonged release HPMC capsule 12mg and allopurinol tablet 300mg, as a free combination, fasted state.
- Treatment 2: verinurad/allopurinol FDC capsule 12/300 mg, fasted state.
- Treatment 3: verinurad/allopurinol FDC capsule 12/300 mg, fed state.
- Treatment 4: verinurad prolonged release HPMC capsule 12mg and allopurinol tablet 300mg, as a free combination, fed state.
- Treatment 5: verinurad prolonged release gelatin capsule 12 mg, fasted state.

All subjects will be instructed to drink approximately 2 L to 2.5 L of liquid a day, starting on Day -2 and throughout the stay at the clinic.

[figure not shown]
Subjects will follow an overnight fast of at least 10 hours before the dosing procedures: for the fed dosing, a high-fat, high-calorie breakfast (see Section 0) will be served 30 minutes before the planned administration of IMP, and is to be consumed in full at least 5 minutes before dosing; for the fasted dosing, no breakfast will be served. A meal can be given 4 hours after administration of IMP for both dosing states.

Details on IMP administration and food and fluid restrictions in relation to IMP administration are provided in Section 5.4.3.

The study flow-chart is presented in Figure 3-1. The SoA displaying assessments/tasks and time-points is presented in Table 3-1.

The study design is deemed appropriate for conduct in healthy volunteers during the COVID-19 pandemic (Section 3.3.3).

Figure 3-1 Study Flow Chart

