5.1.1. Procedures for Randomisation

Upon completion of the randomisation requirements specifications form, the randomisation will be produced by Parexel according to the AstraZeneca randomisation system.

Subjects will be randomised to treatment sequences in a ratio of 1:1:1:1:1 so that all subjects will receive all formulations. The reference product (capsule and tablet as free combination) (Treatments 1 and 4) and the test product (FDC or monotherapy capsule) (Treatments 2 and 3) and a prolonged release gelatin capsule (Treatment 5) will be given under fasted and/or fed conditions as per study design (see Section 3.1).

The randomisation will be completed using consecutive randomisation codes.

The number of subject identifiers generated for the study will account for the number of randomised subjects per the sample size calculation (N = 25) (see Section 11.4) as well as providing sufficient randomisation numbers for replacements. For this study, a total of

25 × 2 subject identifiers will be randomly assigned to the treatment sequences: 12345, 23451, 34512, 45123, and 51234.

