11.1.2. Pharmacokinetic Analysis Set

The PK analysis set will include all subjects in the safety analysis set who received a verinurad + allopurinol (or verinurad alone for Treatment 5) dose and who have at least 1 quantifiable post-dose plasma concentration. In case of an important protocol deviation or event, affected PK data will be excluded from the descriptive and inferential statistical

analyses, but will still be included in the study result listings. For the formal relative bioavailability evaluations, only subjects who provide eligible PK data for both Test and Reference treatments can be included for each comparison.

Data for a subject may be excluded from the descriptive and inferential statistical analyses as a result of the following:

- Where a subject experienced vomiting at or before median t_{max} .
- Where the pre-dose concentration for an analyte is $> 5\%$ of C_{max} in a specific PK sampling period

The exclusion of any subjects or any PK concentrations or parameters from the descriptive or inferential statistical analyses, or of any time-points from the PK parameter non-compartmental analysis, will be discussed and agreed with the AstraZeneca CPS prior to handover of the final PK parameters to programming.

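### The five cyclic sequences are not balanced for first-order carry-over, so residual oxypurinol can only raise the Treatment 2 vs 1 (primary) and 4 vs 1 ratios; Williams sequences would largely remove this at little cost

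*Protocol*

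**What the plan says.** The sequences are fixed in three places: the synopsis, Section 5.1.1 and Section 11.4. Section 11.4 reads: "Twenty-five subjects will be equally randomised to 5 treatment sequences: 12345, 23451, 34512, 45123, and 51234". Section 5.1.1 applies the same list to the randomisation numbers: "subject identifiers will be randomly assigned to the treatment sequences: 12345, 23451, 34512, 45123, and 51234".

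Other parts of the protocol that bear on the point:

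- **Treatments (Section 3.1).** Treatments 1 to 4 contain allopurinol. Treatment 5 is verinurad alone, and Table 3-1 takes no allopurinol or oxypurinol samples in it.
- **Primary outcome (Table 2-1).** AUC and Cmax of oxypurinol are primary measures, alongside those of verinurad and allopurinol, for the fasted comparison of Treatment 2 with Treatment 1.
- **Model (Section 11.2.7).** Sequence, period and treatment, with subject within sequence as random. There is no carry-over term.
- **Washout (Section 3.1).** "There will be a minimum washout period of 5 days between each dose administration".
- **Half-life (Section 1.1.1.1).** 13 h for verinurad with normal renal function. None is given for oxypurinol.
- **Safeguard (Section 11.1.2).** Data may be excluded in this case: "Where the pre-dose concentration for an analyte is $> 5\%$ of" Cmax. The wording is permissive.

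**The concern.** A crossover that relies on washout alone is sound if the washout is long enough for every analyte. It is also more robust if each treatment follows each of the others about equally often, because leftover drug then affects all treatments alike. Here the protocol supports the 5-day gap for verinurad but offers nothing for oxypurinol, and the sequence set gives no second line of defence.

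The arrangement also falls badly for the primary comparison. Within the pair, the fixed-dose capsule (Treatment 2) is the one measured on top of any residue, and the free combination (Treatment 1) always comes directly after the only treatment without allopurinol. Residual oxypurinol would read as higher bioavailability of the capsule. In 4 vs 1 it would read as a food effect. More subjects would not dilute the bias, because it comes from the sequence list itself.

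**Working it through.** **1. The plan's own figure.** Inputs from Section 11.4: "20 subjects randomised to 5 sequences in a reduced Latin square", "intra-subject variability of 24% for C_{max} of verinurad", "intra-subject variability of 14.7% for AUC of verinurad".

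- σ_w = √ln(1 + CV²) = 0.2366 (Cmax) and 0.1462 (AUC).
- SE = σ_w·√(2/20) = 0.0748 and 0.0462.
- With 72 error df, the probability that the 90% CI lies within 0.7–1.43 (Cmax) is 99.8%, and within 0.8–1.25 (AUC) 99.8%. With 18 df both are 99.7%.

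The claims of more than 90% and more than 95% hold. The sample size is not in question.

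**2. Predecessors.** In Periods 2 to 5 only 1→2, 2→3, 3→4, 4→5 and 5→1 occur, each 20 times with 25 subjects. The other 15 ordered pairs never occur.

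**3. Weight of carry-over.** Each treatment appears once per period across the five sequences: once in Period 1 with no predecessor and four times after its fixed predecessor. In the planned model:

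- bias(2 vs 1) = 0.8 × (λ₁ − λ₅)
- bias(4 vs 1) = 0.8 × (λ₃ − λ₅)

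Here λ is the log-scale carry-over from the named predecessor. For oxypurinol λ₅ = 0, so both biases are positive. Leaving out the unsampled Treatment 5 periods does not change the weight.

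**4. Separability.** With 25 subjects the variance of a treatment contrast is 0.080 σ² without carry-over terms and 0.507 σ² with them: 0.507/0.080 = 6.3. The effects can be separated, but only through Period 1 and at that price.

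**5. Size.** The oxypurinol half-life h is an assumption, shown as a range. With mono-exponential decline, the share of one dose's AUC left after 120 h is r = 2^(−120/h). Example at 25 h: r = 2^(−4.8) = 3.6%, and 0.8 × ln(1.036) = 0.028. The table fits the planned model to Treatments 1 to 4 with the residue of all earlier periods included. That takes in Treatment 4 two periods before Treatment 1, at least 10 days back, and makes 2 vs 1 slightly smaller than the one-step formula.

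| Assumed half-life (h) | 15 | 20 | 25 | 30 | 40 |
|---|---|---|---|---|---|
| 2 vs 1, cyclic | +0.3% | +1.2% | +2.8% | +4.7% | +8.9% |
| 4 vs 1, cyclic | +0.3% | +1.2% | +2.9% | +5.0% | +9.8% |
| 2 vs 1, Williams 3:2 | +0.03% | +0.1% | +0.3% | +0.6% | +1.3% |

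Under the cyclic list, 3 vs 2 is biased by at most 0.07% at 15 to 25 h (0.76% at 40 h), and 3 vs 4 by less than 0.07% throughout. These are AUC figures; Cmax was not modelled.

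**6. Verinurad.** 120/13 = 9.2 half-lives, so the residue is 2^(−9.2) = 0.17%, which is negligible.

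**7. The 5% rule.** Measured from a peak assumed at 4 h, 2^(−116/h) = 0.05 gives h = 116/log₂20 = 26.8 h. Below about 27 h the rule does not act, and the 2 vs 1 bias there is at most about 3.5%. Above it, exclusions would fall almost only on Treatments 2 to 4. Section 11.1.2 requires eligible data for both treatments of a comparison, so each exclusion costs the pair.

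**The case against.** A Latin square with a washout is a recognised design, and several points limit the concern.

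- **Full aliasing.** A reader might infer that treatment and carry-over cannot be told apart. That is not so. Period 1 has no predecessor and all five planned contrasts stay estimable, though at 6.3 times the variance.
- **Every comparison.** A reader might extend the bias to all comparisons. The calculation does not support this: oxypurinol residue nearly cancels in 3 vs 2 and 3 vs 4, and 5 vs 2 concerns verinurad only.
- **Size.** The range runs from trivial to material and rests on an unstated half-life. For scale, the 90% CI half-width for AUC with 20 subjects at 14.7% variability is 1.666 × 0.0462 = 0.077 on the log scale.
- **Safeguard.** The larger biases lie where the 5% rule can act. A reader might say that the rule would remove the affected data, but the text only permits exclusion. It neither guarantees protection nor guarantees loss of data.
- **Use of the result.** Section 11.2.1 calls the study explorative, and no bioequivalence decision rule is stated. Serum uric acid is only summarised descriptively, so no planned contrast there is affected.

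These points narrow the concern to oxypurinol in 2 vs 1 and 4 vs 1 and lower its weight. They do not answer it: the direction of the bias is fixed, the washout is not justified for this analyte, and the optional rule leaves smaller residues untouched.

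**Conclusion.** The point holds in a limited form. The sequence list is not balanced for first-order carry-over, and under the planned model residual oxypurinol biases 2 vs 1 and 4 vs 1 upward only. The imbalance and its direction follow from the protocol alone.

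The size does not. It is +0.3% to +8.9% for 2 vs 1 and +0.3% to +9.8% for 4 vs 1 over assumed half-lives of 15 to 40 h, with mono-exponential decline, gaps of exactly the 5-day minimum and no exclusions under the 5% rule. At the low end it would not matter. At the high end it exceeds the expected half-width of the confidence interval.

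This should be fixed because the remedy is cheap and must be in place before randomisation; adjusting afterwards costs too much precision. Confidence is moderate.

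**What to change.** In the synopsis, Section 5.1.1 and Section 11.4, replace the five sequences with the two Williams squares for five treatments:

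- 12534, 23145, 34251, 45312, 51423, with 3 subjects per sequence (15)
- 43521, 54132, 15243, 21354, 32415, with 2 subjects per sequence (10)

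This keeps 25 subjects, five periods, the washout and the model. Each treatment still occurs 5 times in each period, and each ordered pair occurs 4 or 6 times. The unadjusted contrast variance stays at 0.080 σ², and with carry-over terms it is 0.085 to 0.086 σ² instead of 0.507 σ². Section 11.4 should describe the new design and drop the equal-allocation wording.

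**Cost.** An amendment to the sequence text and a new randomisation list, including the spare numbers for replacements. No extra subjects, visits or samples are needed.

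**Downside.** There are ten sequences to manage, and 3:2 instead of equal allocation. Dropouts can disturb the balance further. Carry-over is balanced, not removed: biases of under 1% remain in 3 vs 2 and 3 vs 4 over the assumed range.

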12. LEGAL AND ADMINISTRATIVE ASPECTS

12.1. Archiving of Study Documents

All source documents generated in connection with the study will be retained in the limited access file storage area, respecting the privacy and confidentiality of all records that could identify the subjects. Direct access is allowed only for authorised people for monitoring and auditing purposes. Source documents will be handled, stored and archived according to in-house procedures.

The Investigator's Site File will be archived by the CRO for 25 years after completion of the study.

12.2. Publication of Study Results

All of the study information and data collected during the study are confidential and the property of AstraZeneca. After completion of the study, AstraZeneca may prepare a joint publication with the Investigator. The Investigator must undertake not to submit any data from this CSP for publication without prior consent of AstraZeneca at a mutually agreed time.

Authorship will be determined by mutual agreement and in line with International Committee of Medical Journal Editors authorship requirements.

12.3. Clinical Study Report

An integrated CSR will be prepared in accordance with the standards of the ICH guideline for structure and content of CSRs (ICH E3). Copies of the CSR will be provided to the IEC and the national regulatory authority in accordance with regulatory requirements and Parexel SOPs. In the event of premature termination of the study or other conditions specified in ICH E3, an abbreviated CSR may be prepared.

14. APPENDICES

Appendix A Additional Safety Information

Further Guidance on the Definition of a Serious Adverse Event

Life-threatening

“Life-threatening” means that the subject was at immediate risk of death from the AE as it occurred, or it is suspected that use or continued use of the product would result in the subject’s death. “Life-threatening” does not mean that had an AE occurred in a more severe form it might have caused death (eg, hepatitis that resolved without hepatic failure).

Hospitalisation

Outpatient treatment in an emergency room is not in itself a SAE, although the reasons for it may be (eg, bronchospasm, laryngeal oedema). Hospital admissions and/or surgical operations planned before or during a study are not considered AEs if the illness or disease existed before the subject was enrolled in the study, provided that it did not deteriorate in an unexpected way during the study.

Important Medical Event or Medical Intervention

Medical and scientific judgment should be exercised in deciding whether a case is serious in situations where important medical events may not be immediately life-threatening or result in death, hospitalisation, disability or incapacity but may jeopardise the subject or may require medical intervention to prevent 1 or more outcomes listed in the definition of serious. These should usually be considered as serious.

Simply stopping the suspect drug does not mean that it is an important medical event; medical judgment must be used.

Examples of such events are:

- Angioedema not severe enough to require intubation but requiring intravenous hydrocortisone treatment.
- Hepatotoxicity caused by paracetamol/acetaminophen overdose requiring treatment with N-acetyl cysteine.
- Intensive treatment in an emergency room or at home for allergic bronchospasm.
- Blood dyscrasias (eg, neutropenia or anaemia requiring blood transfusion) or convulsions that do not result in hospitalisation.
- Development of drug dependency or drug abuse.

A Guide to Interpreting the Causality Question

The following factors should be considered when deciding if there is a “reasonable possibility” that an AE may have been caused by the IMP.

- Time course / Exposure to suspect drug:

Has the subject actually received the suspect drug? Did the AE occur in a reasonable temporal relationship to the administration of the suspect drug?

- Consistency with known drug profile:

Was the AE consistent with the previous knowledge of the suspect drug (pharmacology and toxicology) or drugs of the same pharmacological class? OR, could the AE be anticipated from its pharmacological properties?

- Dechallenge experience:

Did the AE resolve or improve on stopping or reducing the dose of the suspect drug?

- No alternative cause:

The AE cannot be reasonably explained by other etiology such as the underlying disease, other drugs, other host or environmental factors.

- Rechallenge experience:

Did the AE reoccur if the suspected drug was reintroduced after having been stopped?

Note: AstraZeneca would not normally recommend or support a rechallenge.

- Laboratory tests:

A specific laboratory investigation (if performed) has confirmed the relationship?

In difficult cases, other factors could be considered such as:

- Is this a recognised feature of overdose of the drug?
- Is there a known mechanism?

Causality of “related” is made if following a review of the relevant data, there is evidence for a “reasonable possibility” of a causal relationship for the individual case. The expression “reasonable possibility” of a causal relationship is meant to convey, in general, that there are facts (evidence) or arguments to suggest a causal relationship.

The causality assessment is performed based on the available data including enough information to make an informed judgment. With limited or insufficient information in the case, it is likely that the event(s) will be assessed as “not related”.

Causal relationship in cases where the disease under study has deteriorated due to lack of effect should be classified as no reasonable possibility.

Appendix B International Airline Transportation Association 6.2 Guidance Document

Labelling and Shipment of Biohazard Samples

International Airline Transportation Association classifies biohazardous agents into 3 categories (http://www.iata.org/whatwedo/cargo/dangerous_goods/infectious_substances.htm). For transport purposes the classification of infectious substances according to risk groups was removed from the Dangerous Goods Regulations in the 46th edition (2005). Infectious substances are now classified either as Category A, Category B or Exempt. There is no direct relationship between Risk Groups and Categories A and B.

Category A Infectious Substances are infectious substances in a form that, when exposure to it occurs, is capable of causing permanent disability, life-threatening or fatal disease in otherwise healthy humans or animals. Category A pathogens are for example, Ebola and Lassa Fever viruses. Category A pathogens:

Are to be packed and shipped in accordance with IATA Instruction 602.

Category B Infectious Substances are infectious substances that do not meet the criteria for inclusion in Category A. Category B pathogens are for example, hepatitis A, B, C, D and E viruses, and HIV types 1 and 2. They are assigned the following UN number and proper shipping name:

- UN 3373 – Biological Substance, Category B
- Are to be packed in accordance with UN3373 and IATA Instruction 650.

Exempt refers to all other materials with minimal risk of containing pathogens.

- Clinical trial samples will fall into Category B or Exempt under IATA regulations.
- Clinical trial samples will routinely be packed and transported at ambient temperature in IATA 650 compliant packaging.
(http://www.iata.org/whatwedo/cargo/dangerous_goods/infectious_substances.htm)
- **Biological samples transported in dry ice require additional dangerous goods specification for the dry ice content.**
- International Airline Transportation Association compliant courier and packaging materials should be used for packing and transportation. Packing should be done by an IATA certified person, as applicable.
- Samples routinely transported by road or rail are subject to local regulations which require that they are also packed and transported in a safe and appropriate way to contain any risk of infection or contamination by using approved couriers and packaging / containment materials at all times. The IATA 650 biological sample containment standards are encouraged wherever possible when road or rail transport is used.

Appendix C Actions Required in Cases of Combined Increase of Aminotransferase and Total Bilirubin - Hy's Law

C 1 Introduction

This Appendix describes the process to be followed in order to identify and appropriately report PHL cases and HL cases. It is not intended to be a comprehensive guide to the management of elevated liver biochemistries.

During the course of the study the Investigator will remain vigilant for increases in liver biochemistry. The Investigator is responsible for determining whether a subject meets potential PHL criteria at any point during the study.

All sources of laboratory data are appropriate for the determination of PHL and HL events; this includes samples taken at scheduled study visits and other visits including central and all local laboratory evaluations even if collected outside of the study visits; for example, PHL criteria could be met by an elevated ALT from a central laboratory and/or elevated total bilirubin (TBL) from a local laboratory.

The Investigator will also review AE data (for example, for AEs that may indicate elevations in liver biochemistry) for possible PHL events.

The Investigator participates, together with AstraZeneca clinical project representatives, in review and assessment of cases meeting PHL criteria to agree whether HL criteria are met. HL criteria are met if there is no alternative explanation for the elevations in liver biochemistry other than Drug-Induced Liver Injury (DILI) caused by the IMP.

The Investigator is responsible for recording data pertaining to PHL/HL cases and for reporting SAEs and AEs according to the outcome of the review and assessment in line with standard safety reporting processes.

C 2 Definitions

Potential Hy's Law

AST or ALT $\geq 3 \times$ ULN **together with** TBL $\geq 2 \times$ ULN at any point during the study following the start of study medication irrespective of an increase in ALP.

Hy's Law

AST or ALT $\geq 3 \times$ ULN **together with** TBL $\geq 2 \times$ ULN, where no other reason, other than the IMP, can be found to explain the combination of increases, eg, elevated ALP indicating cholestasis, viral hepatitis, another drug.

For PHL and HL the elevation in transaminases must precede or be coincident with (ie, on the same day) the elevation in TBL, but there is no specified timeframe within which the elevations in transaminases and TBL must occur.

C 3 Identification of Potential Hy's Law Cases

In order to identify cases of PHL it is important to perform a comprehensive review of laboratory data for any subject who meets any of the following identification criteria in isolation or in combination:

- $AST \geq 3 \times ULN$
- $ALT \geq 3 \times ULN$
- $TBL \geq 2 \times ULN$

The Investigator will without delay review each new laboratory report and if the identification criteria are met will:

- Notify the AstraZeneca representative
- Determine whether the subject meets PHL criteria (see Section 2 within this appendix for definition) by reviewing laboratory reports from all previous visits
- Promptly enter the laboratory data into the laboratory CRF module(s)

C 4 Follow-Up

C 4.1 Potential Hy's Law Criteria not met

If the subject does not meet PHL criteria the Investigator will:

- Inform the AstraZeneca representative that the subject has not met PHL criteria
- Perform follow-up on subsequent laboratory results according to the guidance provided in the CSP

C 4.2 Potential Hy's Law Criteria met

If the subject does meet PHL criteria the Investigator will:

- Notify the AstraZeneca representative who will then inform the central Study Team
- Within 1 day of PHL criteria being met, the Investigator will report the case as an SAE of PHL; serious criteria "Important medical event" and causality assessment "yes/related" according to CSP process for SAE reporting

- For subjects that met PHL criteria prior to starting IMP, the Investigator is not required to submit a PHL SAE unless there is a significant change[‡] in the subject's condition
- The Study Physician contacts the Investigator, to provide guidance, discuss and agree an approach for the study subjects' follow-up (including any further laboratory testing) and the continuous review of data
 - Subsequent to this contact the Investigator will:
 - Monitor the subject until liver biochemistry parameters and appropriate clinical symptoms and signs return to normal or baseline levels, or as long as medically indicated. Completes follow-up SAE Form as required.
 - Investigate the etiology of the event and perform diagnostic investigations as discussed with the Study Physician. This includes deciding which the tests available in the HL laboratory kit should be used (if applicable).
 - Complete the 3 liver CRF modules as information becomes available.

C 5 Review and Assessment of Potential Hy's Law Cases

The instructions in this section should be followed for all cases where PHL criteria are met.

As soon as possible after the biochemistry abnormality was initially detected, the Study Physician contacts the Investigator in order to review available data and agree on whether there is an alternative explanation for meeting PHL criteria other than DILI caused by the IMP, to ensure timely analysis and reporting to health authorities within 15 calendar days from the date the PHL criteria were met. The AstraZeneca Global Clinical Lead or equivalent and Global Safety Physician will also be involved in this review together with other subject matter experts as appropriate.

According to the outcome of the review and assessment, the Investigator will follow the instructions below.

Where there is an agreed alternative explanation for the AST or ALT and TBL elevations, a determination of whether the alternative explanation is an AE will be made and subsequently whether the AE meets any criteria for a SAE:

- If the alternative explanation is **not** an AE, record the alternative explanation on the appropriate CRF module(s)

[‡] A 'significant' change in the subject's condition refers to a clinically relevant change in any of the individual liver biochemistry parameters (ALT, AST or total bilirubin) in isolation or in combination, or a clinically relevant change in associated symptoms. The determination of whether there has been a significant change will be at the discretion of the Investigator, this may be in consultation with the Study Physician if there is any uncertainty.

- If the alternative explanation is an AE/SAE: update the previously submitted PHL SAE and AE CRF entries accordingly with the new information (reassessing event term; causality and seriousness criteria) following the AstraZeneca standard processes

If it is agreed that there is **no** explanation that would explain the AST or ALT and TBL elevations other than the IMP:

- Send updated SAE (report term “Hy’s Law”) according to AstraZeneca standard processes
 - The “Medically Important” seriousness criterion should be used if no other seriousness criteria apply
 - As there is no alternative explanation for the HL case, a causality assessment of “related” should be assigned

If there is an unavoidable delay of over 15 calendar days in obtaining the information necessary to assess whether the case meets the criteria for HL, then it is assumed that there is no alternative explanation until such time as an informed decision can be made:

- Provide any further update to the previously submitted SAE of PHL (report term now “Hy’s Law case”), ensuring causality assessment is “related to IMP” and seriousness criterion is “medically important”, according to CSP process for SAE reporting
- Continue follow-up and review according to agreed plan. Once the necessary supplementary information is obtained, repeat the review and assessment to determine whether HL criteria are still met. Update the previously submitted PHL SAE report following CSP process for SAE reporting, according to the outcome of the review and amending the reported term if an alternative explanation for the liver biochemistry elevations is determined.

C 6 Laboratory Tests

The list below represents the standard, comprehensive list of follow-up tests which are recommended but not mandatory when using a central laboratory. For studies using a local laboratory, the list may be modified based on clinical judgment. Any test results need to be recorded.

Hy's Law laboratory kit for central laboratories (18 December 2018)

Additional standard biochemistry and coagulation tests	GGT LDH Prothrombin time INR	
Viral hepatitis	IgM anti-HAV IgM and IgG anti-HBc HBsAg HBV DNA	IgG anti-HCV HCV RNA* IgM anti-HEV HEV RNA
Other viral infections	IgM & IgG anti-CMV IgM & IgG anti-HSV IgM & IgG anti-EBV	
Alcoholic hepatitis	Carbohydrate deficient transferrin (CD-transferrin)	
Autoimmune hepatitis	Antinuclear antibody (ANA) Anti-Liver/Kidney Microsomal Ab (Anti-LKM) Anti-Smooth Muscle Ab (ASMA)	
Metabolic diseases	alpha-1-antitrypsin Ceruloplasmin Iron Ferritin Transferrin Transferrin saturation	

* HCV RNA is only tested when anti-HCV is positive or inconclusive

REFERENCES


Appendix D Actions Required in Cases of a Renal-related or Urolithiasis Treatment-emergent Adverse Event or a Serum Creatinine Elevation

During the course of the study, the Investigator will remain vigilant for symptoms or signs of renal-related events, kidney stone events or changes in renal function.

D 1 Signs and Symptoms Suggestive of Urolithiasis

After initiation of study medication, if a subject experiences signs or symptoms suggestive of nephrolithiasis (eg, flank pain or haematuria), he/she should be evaluated by a physician and serum creatinine, blood urea nitrogen, and urinalysis should be measured via central laboratory testing (preferred) and/or local laboratory testing, as appropriate, to determine renal function. Imaging (intravenous urogram, renal ultrasound, or magnetic resonance imaging) is recommended to confirm or exclude any urinary tract calculus. Abnormal results should be treated as medically appropriate by the treating physician. All symptoms, testing, and results will be documented in source documents and ClinBase™.

If a subject develops a urinary tract calculus (as confirmed and documented by imaging or passage of a stone) at any time during the study, the subject will discontinue randomised study medication and be encouraged to remain in the study for continued safety assessments. If the urinary tract calculus is passed, it should be collected and submitted to pathology for analysis of chemical composition.

D 2 Deterioration of Renal Function

The Investigator should assess subjects exhibiting elevated serum creatinine carefully to determine the most likely cause for the deterioration of renal function. Following a thorough assessment, the subject should be managed according to local medical practice. Potentially-treatable causes such as volume depletion, hypotension etc., should be corrected before following the recommendations given below.

Serum Creatinine Increase to ≥ 1.5 -fold from Baseline

- Assess the subject to identify and manage any potential contributing factor. Correct any dehydration and ensure the subject is well hydrated prior any future evaluation.
- Contact the Sponsor's lead physician for advice and to discuss discontinuation of study medication.
- Assess creatinine daily if the elevation is detected while the subject is admitted to the Clinical Unit, and otherwise weekly.
- Subsequent management will depend on the repeat measurement(s):
 - If serum creatinine < 1.5 -fold of baseline value for 2 successive measurements, the subject may restart/continue with study treatment on the original study visit schedule.

- If repeat serum creatinine is ≥ 1.5 -fold of baseline, the subject should be evaluated every week until normalisation. The randomised treatment should be permanently discontinued.
